- Adverse events (recorded at supervised exercise sessions or reported from home sessions)
- Time commitment per participant (for participants, calculated as sum of hours exercising; for staff, calculated as [hours spent supervising exercise / number of individuals supervised simultaneously + hours spent scheduling and/or coordinating for that participant])
- Qualitative feasibility collected via narrative survey of participants and staff

B. Description of Population to be Enrolled:

Men and women ages 18-65 with deployment-related respiratory disease and symptoms of exertional dyspnea or exercise intolerance residing in the Veterans Integrated Service Network (VISN) 19 and receiving some or all of their care at VA medical facilities throughout the Eastern Colorado Health Care System (ECHCS) will be recruited. We will enroll up to 12 eligible veterans.

- **Inclusion Criteria:**

- Deployment of ≥ 30 days to Iraq, Afghanistan, Kuwait, Saudi Arabia, Bahrain, Qatar, United Arab Emirates, Kyrgyzstan, or Djibouti after September 2001(11)
- New onset of cough, shortness of breath, chest tightness/wheezing, dyspnea on exertion or exercise intolerance which started during or after deployment(11)
- Definite or probable distal lung disease (≥ 1 hyperinflation, emphysema, bronchiolitis, small airways inflammation, peribronchiolar fibrosis, or granulomatous pneumonitis on surgical lung biopsy; or ≥ 2 centrilobular nodularity, air trapping, mosaicism, or bronchial wall thickening on chest CT),(11) definite or probable deployment-related asthma (≥ 1 increase in post-bronchodilator forced expiratory volume in 1 second [FEV₁] $\geq 12\%$ and ≥ 200 cc, or methacholine challenge with PC₂₀ FEV₁ ≤ 16 mg/mL)(11) or unexplained dyspnea on exertion or exercise intolerance despite noninvasive testing including pulmonary function testing, methacholine challenge, transthoracic echocardiography, and/or chest computed tomography(9, 13)
- Current symptoms of dyspnea on exertion or exercise intolerance
- Residence <90 miles from RMR VA and ability / willingness to attend in-person HIIT sessions and research visits

- **Exclusion criteria:**

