The proposed study is a single-arm clinical trial to generate pilot data regarding the safety, feasibility and efficacy of an exercise intervention. Participants will complete a baseline assessment (Visits 1A +/- 1B) at 0 weeks followed by up to 12 weeks of HIIT intervention followed by a repeat assessment (Visits 2A +/- 2B). An overview of the study protocol is provided in Figure 1.

Figure 1: Protocol Overview

Visits 1A/1B and 2A/2B: Visits 1A and 2A will be performed in the inpatient unit of the Clinical and Translational Research Center at the University of Colorado. Each visit will include administration of SF-36 questionnaire, spirometry, and a cardiopulmonary exercise test. Peripheral IV will be placed for the purpose of venous blood draws for complete blood count, ferritin and untargeted metabolomics analysis.(1) Radial arterial line will be placed for continuous blood pressure monitoring and measurement of arterial blood gas and lactate. Participants will be oriented to VO2max testing protocol. Baseline fitness will be assessed by questioning to determine step protocol. Once arterial line is in place, participants will complete a symptom-limited CPET on an upright stationary bicycle. Workload will begin at 0 Watts and increase every minute by 10-30 W (based upon pre-testing questioning) to achieve volitional exhaustion with maximum workload at 8-12 minutes.(22) Heart rate and rhythm, blood pressure, oxygen saturation, and gas exchange parameters (VO2, VCO2, and minute ventilation) will be continuously measured. Borg RPE, arterial blood gas and lactic acid will be measured at rest, every 4 minutes during exercise, and at peak exertion. Attainment of a high-quality VO2max will be determined based upon achieving one or more of the following: a plateau in VO2; attainment of predicted VO2max, work rate, or heart rate; respiratory exchange ratio >1.15, and Borg Scale rating 9-10 on a 0-10 scale.(6) Peripheral venous blood draw for untargeted metabolomics analysis will be repeated at peak exercise.

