Recruitment of participants: This pilot study seeks to study 12 individuals in a one-year timeframe. [name], a PI and an expert in deployment-related respiratory disease,(11, 29-31) is the director of the Rocky Mountain Regional Post Deployment Cardiopulmonary Evaluation Network. Her presence lends feasibility to this proposal's participant recruitment. With >200 patients enrolled in research initiatives through the RMR PDCEN and Chest Exposure Clinic and based on the research team's experience recruiting for similar exercise assessment protocols (COMIRB #16-1635, 17-1042, 19-1141, 21-4354),(8, 32, 33) a sample size of 12 is feasible to recruit and study in one year.

Heterogeneity of study population: Deployment-related respiratory disease is by nature a heterogeneous condition. While narrowing the study population to a particular pathophysiologic subgroup might strengthen the study's conclusions, for the purpose of collecting pilot data in the specified one-year timeframe this study will include individuals with multiple phenotypes (i.e. distal lung disease, asthma and unexplained dyspnea; see "Inclusion Criteria"). However, to minimize additional heterogeneity participants will be carefully screened and excluded for comorbid conditions (see "Exclusion Criteria"). Additionally, a heterogenous BMI range is included again for the purpose of collecting pilot data in the specified one-year timeframe. BMI will be tested as a covariate in the statistical analysis, and based upon these analyses future studies may be designed with a more narrow BMI inclusion range.

Lack of control group: The lack of a control group will limit conclusions regarding efficacy of HIIT intervention. However, for the purpose of collecting pilot data in the proposed timeframe this is felt to be appropriate. This study will instead inform future larger randomized controlled trials of exercise interventions in this population.

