Feasibility of exercise training program: A three-week familiarization / physiologic adaptation period has been built into the HIIT program to maximize the likelihood of participants being able to successfully perform the exercise training program. However, there is still the possibility of individuals being unable to complete the full intended training program due to injury or other reasons. Successful completion of HIIT sessions (including meeting target heart rate) will be assessed by the study team at least every 4 weeks. If an individual demonstrates >3 sessions over a 4-week period in which they fail to meet the exercise prescription, a study team member will discuss with the participant barriers to meeting the exercise prescription and help identify ways to address those barriers as appropriate. If an individual develops an injury which prevents them from completing the prescribed exercise program, they will be transitioned to a continuous exercise training regimen if possible (i.e. substituting "light exercise" training sessions for HIIT sessions) until able to resume HIIT, at which time they will begin HIIT with a repeat three-week familiarization / physiologic adaptation period. If they are unable to complete continuous exercise training, they will discontinue exercise training until able to resume. Completion rates of HIIT and continuous exercise training will be assessed as part of the analysis of the study (Aim 2).

E. Data Analysis Plan:

Specific Aim 1:

Hypothesis 1A: Pulmonary vascular remodeling resulting from prior airborne hazards exposures increases exertional pulmonary arterial pressure and right ventricular afterload, resulting in compromised right ventricular exertional performance with abnormal oxygen pulse, ventilatory inefficiency and increased dead space fraction on CPET and increased pulmonary artery systolic pressure during exertion (relative to healthy population norms).(4) Oxygen pulse, ventilatory efficiency, and dead space fraction will be analyzed using descriptive statistics. Results will be presented in reference to healthy population norms (ATS/ACCP guidelines).(6) Pulmonary artery systolic pressure will be analyzed using descriptive statistics. Results will be presented in reference to healthy population norms (American Society of Echocardiography guidelines).(5)

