Hypothesis 1B: Increased right ventricular afterload causes maladaptive right ventricular remodeling which is reflected by increased glycolytic metabolites (compared to a reference healthy population).(2, 3) Metabolomics partial least squares discriminant analysis and t-test or ANOVA will be performed. Exercise metabolomics data collected in a healthy population (COMIRB 21-4354) will be used as a reference.

Hypothesis 1C: Impaired right ventricular performance contributes to reduced maximum oxygen consumption (VO2max) relative to healthy population norms, dyspnea and impaired health-related quality of life. VO2max will be analyzed using descriptive statistics and presented in reference to healthy population norms (ATS/ACCP guidelines).(6) Dyspnea and health-related quality of life will be assessed by SF-36 with scores analyzed by descriptive statistics. Scores will be presented in

reference to disease population references.(34, 35) Linear mixed models will be used to assess the relationship between impaired right ventricular performance as measured by pulmonary artery systolic pressure and VO2max. Covariates including BMI, gender, age and type of deployment-related respiratory disease will be included.

Specific Aim 2:

Hypothesis 2A: *HIIT is safe and feasible among military personnel suffering from deployment-related respiratory disease, with $\geq 80\%$ participation in prescribed sessions.*(8) Attendance will be calculated as (number of supervised sessions attended + unsupervised sessions reported by exercise diary) / total number of supervised + unsupervised sessions. Feasibility will be based upon attendance of $>80\%$ of prescribed exercise sessions, with separate analyses for HIIT sessions, “light exercise” sessions, and combined sessions. Safety/acceptability will be based upon an absence of major adverse events attributable to the exercise training program and $<5\%$ minor adverse events (calculated as the number of adverse events divided by the total number of exercise sessions throughout the program) attributable to the exercise training program.

Hypothesis 2B: *Participants will spend approximately 4.5 hours/week engaged in this program and will report that participation was feasible.* Total hours spent in exercise program will be calculated based upon number of supervised sessions and reported unsupervised sessions. Qualitative assessment of feasibility will be collected via narrative report.

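### Aim 1 (Hypotheses 1A and 1C) reads exercise-test results from Colorado residents only against published norms, with no site-matched healthy reference and no check that the norms apply at the site's elevation

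*Combined protocol and SAP*

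**What the plan says.** Hypotheses 1A and 1C, under Specific Aim 1, are worded as departures from healthy norms: abnormal oxygen pulse, ventilatory inefficiency and increased dead space fraction in 1A, reduced VO2max in 1C.

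- **Comparator for 1A (Data Analysis Plan).** Oxygen pulse, ventilatory efficiency and dead space fraction are described, and "Results will be presented in reference to healthy population norms (ATS/ACCP guidelines"). Pulmonary artery systolic pressure is handled likewise, against echocardiography society norms.
- **Comparator for 1C.** "VO2max will be analyzed using descriptive statistics and presented in reference to healthy population norms (ATS/ACCP guidelines"). There is also an analysis within the sample: "Linear mixed models will be used to assess the relationship between impaired right ventricular performance as measured by pulmonary artery systolic pressure and VO2max".
- **Comparator for 1B.** Here the plan uses a healthy cohort: "Exercise metabolomics data collected in a healthy population (COMIRB 21-4354) will be used as a reference".
- **Where and in whom.** Section III.C: "Visits 1A and 2A will be performed in the inpatient unit of the Clinical and Translational Research Center at the University of Colorado". The inclusion criteria in Section III.B require "Residence <90 miles from RMR VA".
- **What is not said.** Altitude and barometric pressure do not appear. The Potential Scientific Problems section does not discuss whether the norms fit the site; its paragraph on the missing control group deals only with the efficacy of HIIT.

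**The concern.** Aim 1 has no control group, so the published norm is the whole basis for calling a VO2max reduced or ventilation inefficient. If healthy people tested at this site differ systematically from the population behind the norms, that difference is added to every participant's result. It is a bias, and more participants would not remove it.

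Its likely direction is unhelpful. With less inspired oxygen, VO2max falls, and oxygen pulse falls with it if peak heart rate is unchanged. Residents who run a lower PaCO2 have a higher VE/VCO2 at the same dead space. Both shifts resemble what 1A and 1C predict, without any pulmonary vascular disease. Generating hypotheses about such disease is a stated primary objective, and the results are meant to inform a larger investigation. The harm would be a site effect carried forward as a disease signal.

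**Working it through.** **The plan's own figure.** The documents give no figure for the norm comparison. Their only design figure is the Aim 3 sample size for the change in VO2max. It reproduces by the normal approximation: ((1.960 + 1.282) × 1.8 / 2)² = 8.5, rounded up to 9; 9 / 0.90 = 10. It has no bearing on this point.

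**Inputs from the documents.** Colorado test site, local residents, up to 12 participants, published norms as the only reference for the 1A and 1C exercise-test results, and arterial blood gases at rest, every 4 minutes of exercise and at peak.

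**Inputs that are assumptions.** Elevation about 1,600-1,700 m; VO2max loss of 3%, 5% or 10% in healthy residents; percent-predicted VO2max in healthy people normal with mean 100 and SD 12 or 15; abnormal means below 80% or 84% predicted. The plan sets no cut-off. Predicted values are taken as not adjusted for altitude.

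**Step 1: share of healthy local people labelled abnormal.** Share = Φ((cut-off − (100 − loss)) / SD). For example, with cut-off 80, SD 12 and loss 5: Φ((80 − 95)/12) = Φ(−1.25) = 10.6%.

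| Loss | Cut-off 80, SD 12 | Cut-off 80, SD 15 | Cut-off 84, SD 12 | Cut-off 84, SD 15 | Extra people in 12 |
|---|---|---|---|---|---|
| 0% | 4.8% | 9.1% | 9.1% | 14.3% | – |
| 3% | 7.8% | 12.8% | 13.9% | 19.3% | 0.4 to 0.6 |
| 5% | 10.6% | 15.9% | 18.0% | 23.2% | 0.7 to 1.1 |
| 10% | 20.2% | 25.2% | 30.9% | 34.5% | 1.9 to 2.6 |

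Extra people = 12 × (share at that loss − share at no loss), over the four columns. The smallest is 12 × (0.0783 − 0.0478) = 0.4 and the largest is 12 × (0.3085 − 0.0912) = 2.6.

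**Step 2: a different definition of abnormal.** Put the limit at the 5th percentile and let the SD run from 12 to 20. The share is then 5.0% with no shift, 8.2-11.0% at 5 points and 12.6-20.8% at 10 points. In 12 people, 10 points adds 12 × (0.126 − 0.050) = 0.9 to 12 × (0.208 − 0.050) = 1.9. The direction is the same and the size smaller, so the result depends on a cut-off that the plan does not state.

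**Step 3: VE/VCO2.** By the alveolar ventilation equation, VE/VCO2 = 863 / [PaCO2 × (1 − VD/VT)]. With VD/VT at 0.20 (assumed):

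- PaCO2 40: 863 / (40 × 0.80) = 27.0
- PaCO2 37: 863 / (37 × 0.80) = 29.2
- PaCO2 36: 863 / (36 × 0.80) = 30.0

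The rise is 40/37 = 1.08 to 40/36 = 1.11, or 8-11%, with dead space unchanged. The same 30.0 arises at PaCO2 40 if VD/VT is 0.28: 863 / (40 × 0.72) = 30.0. VE/VCO2 alone cannot tell the two apart; PaCO2 and VD/VT can, and the plan measures both.

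**Step 4: which analyses are touched.** A constant offset d changes (result − norm) by d, so the 1A and 1C norm comparisons move. In Aim 3, (post − d) − (pre − d) = post − pre, so it cancels. In the 1C within-sample model, a constant subtracted from every VO2max changes the intercept and not the slope on pulmonary artery pressure.

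**The case against.** The strongest reply is that every quantity behind the size lies outside the documents: elevation, loss of VO2max, residents' PaCO2, the SD and the cut-off. Nor can it be checked here whether the cited norms already deal with altitude. This stands, and it is why the figures are illustrations and why the first step of the fix is to find out.

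Second, Aim 1 is hypothesis-generating and its norm comparisons are descriptive, without a test or a decision rule. This limits the consequence. It does not remove it, because without controls the abnormality label is itself the result.

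Third, the VE/VCO2 part is largely answerable from planned data. Arterial gases are taken, and dead space fraction is a 1A measure in its own right. A rise due only to low PaCO2 would come with a normal dead space fraction, which is not the pattern that 1A predicts. This also stands; what is missing is the instruction to read the measures together.

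Three stronger readings are tempting.

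- *Altitude would explain whatever abnormality is found.* The documents give no basis for a size, and at the small end the effect is less than one person in 12.
- *The 1B healthy cohort is a ready comparator.* The plan says only that it supplies exercise metabolomics data, and the recruitment paragraph lists it among "similar exercise assessment protocols (COMIRB #16-1635, 17-1042, 19-1141, 21-4354"). Neither place says that it holds VO2max or VE/VCO2 values, where it was tested, or how large or fit it is.
- *The efficacy results are compromised.* They are not: a constant offset cancels before and after training.

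**Conclusion.** The point holds as a limited gap. For VO2max, oxygen pulse and ventilatory efficiency, 1A and 1C rely only on published norms, with no site-matched healthy reference and no statement that the norms apply at the test site. Any altitude offset would favour the hypotheses.

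Under the stated assumptions the share of healthy local people labelled abnormal rises from 5-14% to 8-19% at a 3% loss and to 20-35% at a 10% loss, or about 0.4 to 2.6 extra people in 12. VE/VCO2 rises 8-11% if PaCO2 is 36-37 and not 40. No size was worked out for oxygen pulse. The direction is plausible; the magnitude cannot be fixed from the documents and would be nil if the predicted values already allow for elevation.

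The Aim 3 comparisons are unaffected by a constant offset, and such an offset does not by itself create the 1C association. This is a cheap improvement to the interpretation of Aim 1, not a flaw in the trial's design.

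**What to change.** Amend the Data Analysis Plan for 1A and 1C as follows.

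1. Name the predicted values to be used and state whether they account for the test site's elevation. If they do not, show VO2max against both the unadjusted norm and a stated altitude-adjusted prediction, the latter as a sensitivity presentation.
2. Report VE/VCO2 beside arterial PaCO2 and dead space fraction at the same time points. Attribute a raised VE/VCO2 to ventilatory inefficiency from vascular disease only where a low PaCO2 does not explain it.
3. Establish whether COMIRB 21-4354 collected exercise-test values at the same site with a comparable protocol. If so, add them as a supplementary local reference and describe differences in age, sex, body size and fitness. If not, say so.

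The cost is analysis wording and, for item 3, access to data from a study already drawn on for 1B. No new procedure or participant is needed. The downsides are that the local cohort may be small, or fitter than this population, which excludes people in a current fitness program. It should therefore supplement the published norms and not replace them. The reported abnormality may also turn out less striking.

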Exercise training and in particular high-intensity interval training (HIIT) improves maximal oxygen uptake (VO₂max) among healthy individuals and those with pulmonary disease.^(7, 15) ^(16, 17) Fitness gains from HIIT may derive from changes in metabolic and protein expression contributing to muscle adaptation as well as cardiovascular adaptations including increased left ventricular compliance and right ventricular remodeling.^(2, 8, 18, 19) For example, in rats the shift to glycolytic metabolism which accompanies pathologic right ventricular remodeling in pulmonary hypertension is attenuated by HIIT,^(2, 3) and pulmonary vascular remodeling and right ventricular function improves after HIIT.^(2, 20) However, whether HIIT improves symptoms or functional capacity in deployment-related respiratory disease has not been investigated. Moreover, given uncertainties regarding mechanisms of deployment-related respiratory disease, recommendations on management of this syndrome in general are lacking.⁽²¹⁾ Therefore, the **primary objectives of this study are: 1) generate hypotheses regarding the role of cardiac and pulmonary vascular abnormalities in contributing to exercise intolerance and 2) generate pilot data regarding the safety, feasibility, and efficacy of HIIT in improving functional capacity and alleviating symptoms in deployment-related respiratory disease.** The results will inform a larger investigation of extrapulmonary mechanisms of symptoms and exercise interventions in deployment-related respiratory disease.

III. Research Methods

A. Outcome Measures:

Primary Outcomes:

- VO₂max
- Health-related quality of life (SF-36)

Secondary Outcomes:

- Gas exchange (oxygen consumption [VO₂], carbon dioxide production [VCO₂] and minute ventilation to generate calculations of oxygen pulse [VO₂/HR], ventilatory efficiency [VE/VCO₂], and dead space fraction [estimated dead space / tidal volume])
- TTE parameters of cardiac function (right ventricular pulmonary artery systolic pressure, mid-cavity diameter, tricuspid annular plane systolic excursion, right ventricular longitudinal strain, left ventricular ejection fraction, transmural peak inflow velocity of early rapid diastolic filling / early diastolic mitral annular velocity [E/e'])
- Peripheral venous blood untargeted metabolomics
- Borg rating of perceived exertion (RPE)
- Participation (attendance at supervised exercise sessions and diary of home sessions)

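### Hypothesis 1C attributes dyspnea and impaired quality of life to right ventricular performance, but the plan relates pulmonary artery systolic pressure only to VO2max and merely describes SF-36

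*Combined protocol and SAP*

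**What the plan says.** All of this is in the Data Analysis Plan, Specific Aim 1, unless stated otherwise.

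- **Hypothesis 1C** names three consequences of impaired right ventricular performance: reduced VO2max, dyspnea and impaired health-related quality of life. VO2max is described against healthy norms and also receives a model: "Linear mixed models will be used to assess the relationship between impaired right ventricular performance as measured by pulmonary artery systolic pressure and VO2max". BMI, gender, age and disease type are covariates.
- **SF-36 under 1C**: "Dyspnea and health-related quality of life will be assessed by SF-36 with scores analyzed by descriptive statistics". The scores are set beside published disease populations. Outcome Measures lists SF-36 as a primary outcome.
- **Hypothesis 1B**: "Increased right ventricular afterload causes maladaptive right ventricular remodeling which is reflected by increased glycolytic metabolites (compared to a reference healthy population". Its analysis is: "Metabolomics partial least squares discriminant analysis and t-test or ANOVA will be performed". The comparator is also given: "Exercise metabolomics data collected in a healthy population (COMIRB 21-4354) will be used as a reference".
- **Hypothesis 1A** describes pulmonary artery systolic pressure (PASP) against echocardiographic norms.
- **Source of PASP**: transthoracic echocardiography (TTE) at Visits 1B and 2B, which Study Design and Research Methods makes optional. Specific Aim 1 likewise says only that TTE may be done.

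**The concern.** Hypothesis 1C is a statement about a relationship. A description of SF-36 scores shows how impaired the participants are, and setting the scores beside other disease populations shows how they compare with those populations. Neither shows whether participants with higher PASP report worse symptoms.

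If the plan is followed as written, low SF-36 scores could be presented under 1C as consistent with a right ventricular mechanism when no result connects the two. Aim 1 exists to generate hypotheses about the cardiac and pulmonary vascular contribution, and the Summary of Knowledge to be Gained says the results will inform larger studies of mechanisms of dyspnea outside the lung. Dyspnea is the outcome that is never set against a right ventricular measure.

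**Working it through.** **Step 1. Match each link asserted in 1C to a planned analysis.**

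| Link asserted from right ventricular performance | Baseline analysis (Aim 1) | Analysis in Aim 3 | Relates it to a right ventricular measure? |
|---|---|---|---|
| to VO2max | Description against norms; model with PASP | Pre/post t-test | Yes |
| to dyspnea (SF-36) | Description | Pre/post t-test | No |
| to quality of life (SF-36) | Description | Pre/post t-test | No |

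PASP itself is described under 1A and compared before and after training under 3A. Each Aim 3 outcome is compared on its own, so Aim 3 does not supply the missing link. The sentence on the mixed model could also be read as making PASP and VO2max joint measures of right ventricular performance. It would then name no outcome, and SF-36 would still be absent.

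**Step 2. Do the same for 1B.** The hypothesis states its comparator, a healthy reference population, and the plan runs that comparison. No right ventricular variable enters it. It therefore tests whether glycolytic metabolites are higher in patients, but not why. Patients are enrolled with distal lung disease, asthma or unexplained dyspnea, and people in a current fitness program are excluded, so the groups may differ in more than afterload.

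**Step 3. The plan's own figure.** The Sample Size section concerns the pre/post change in VO2max, not any association. It reproduces with a paired normal approximation, two-sided: n = (1.8 × (1.960 + 1.282) / 2)² = 8.51, rounded up to 9; 9 / 0.9 = 10. The plan gives no precision for an association with PASP.

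**Step 4. Precision of the missing association.**

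Inputs: an observed Spearman correlation of 0.5 (assumed for illustration); 12 participants as the enrolment ceiling; 6 and 8 participants with TTE as assumptions, since the documents set no minimum.

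Formula, on the Fisher z scale with a usual variance for Spearman's coefficient: tanh( atanh(r) ± 1.96 × √[(1 + r²/2) / (n − 3)] ).

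With r = 0.5, atanh(r) = 0.549 and 1 + r²/2 = 1.125.

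| n with TTE | √[1.125 / (n − 3)] | Half-width (× 1.96) | 95% interval for the correlation |
|---|---|---|---|
| 6 | 0.612 | 1.200 | -0.57 to 0.94 |
| 8 | 0.474 | 0.930 | -0.36 to 0.90 |
| 12 | 0.354 | 0.693 | -0.14 to 0.85 |

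Every interval includes zero, even with TTE in all 12 participants.

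**The case against.** **Aim 1 only generates hypotheses, and 12 people cannot establish a mechanism.** This stands, and it keeps the point minor. But 1C is worded as a contribution of one thing to another, and the plan already models PASP against VO2max in the same people. A scatter plot with an interval asks less of the data than that model.

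**A correlation would not show causation and would omit the covariates of the VO2max model.** This also stands. With one baseline record from each of 12 participants, an intercept, PASP, BMI, gender, age and two terms for three disease types leave 12 − 7 = 5 residual degrees of freedom, so adjustment offers little. The correlation is a way to see the asserted relationship, not to prove it.

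**The measurements do not coincide.** SF-36 is taken at Visit 1A. Exertional TTE is taken at Visit 1B, up to two weeks later, supine and immediately after exercise. The plan also does not say which SF-36 score represents dyspnea. These limits should be reported with the result; they do not remove the gap.

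**A stronger reading: 1B is never tested either.** A reader might infer this because no right ventricular variable enters the metabolite analysis. The documents do not support it: 1B specifies patients against a healthy reference, and that comparison is planned. Nor does the Background's remark on muscle adaptation show that the plan recognises a muscle explanation for a baseline difference. It concerns fitness gains from training and goes on to name cardiovascular adaptations too. A metabolite correlation would need a glycolytic score that the documents do not define, and would not establish afterload as the cause.

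**Conclusion.** The concern holds for 1C. Of its three asserted consequences, one (VO2max) is related to a right ventricular measure; dyspnea and quality of life are not, at baseline or in Aim 3. This rests on reading the planned analyses and on no numerical assumption.

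For 1B the concern reduces to wording: the stated comparator is tested, but a group difference does not identify afterload as its source.

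The size is modest. Nothing here affects the pre/post efficacy comparisons or the safety and feasibility criteria. The added estimate could guide a hypothesis but not confirm one; how wide its interval is depends on how many participants have TTE, which the documents leave open.

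**What to change.** **For 1C, do one of the following.**

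1. Add one exploratory baseline analysis: the Spearman correlation of exertional PASP (Visit 1B TTE) with one SF-36 score named before the data are examined. Report it with a 95% interval and a scatter plot, state how many participants had TTE, and label it hypothesis-generating. The sponsor chooses the score and says what it stands for.
2. Otherwise narrow 1C to the VO2max relationship and report SF-36 as a descriptive finding with no right ventricular attribution.

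**For 1B**, keep the planned analysis and add a sentence: the result is a group difference in glycolytic metabolites between patients and the healthy reference, and does not by itself attribute that difference to right ventricular afterload.

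**Cost.** One correlation or a text edit, plus one sentence. No new procedure or data collection is needed, since PASP (where TTE is done) and SF-36 are already planned. The downside of option 1 is a wide interval that may make the right ventricular account look weaker, and a sample limited to those who accept the optional visit.
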